##### Drug-related risks and safety measures

The nature of the target and the mechanism of action of BI 730357 are well understood from preclinical models. The safety, tolerability, and PK exposure following single-dose administration of BI 730357 have already been established in first-in-human trial 1407.1, at dose levels up to 800 mg, 4-fold higher than the maximum dose level (200 mg) to be evaluated in the current trial. Furthermore, since this is not a First-in-Human trial, the risk is relatively lower.

The pharmacological effects of BI 730357 are dose dependent and no evidence for prolonged or irreversible effects has been observed. Single dose administration of dose levels up to 800 mg BI 730357 are supported by preclinical safety data.

- Extensive safety laboratory testing will be performed with special focus on full blood exam (refer to [Flow Chart](#)).
- A thorough ECG monitoring including 4-hours continuous 3-lead ECG measurement for at least 15 min before drug administration (for baseline assessment) and for 4 hours following drug administration to cover the anticipated period of highest drug exposure, and additional repeated single 12-lead ECGs over 48 hours (during hospital stay) following drug administration. Dose escalation would be stopped as soon as at

least 2 subjects at one dose level showed relevant QT prolongation (refer to Section 3.3.4.3 for details).

- Prior to each dose escalation, a documented safety review will be performed by the principal investigator and the sponsor (clinical trial leader [CTL]). For details, refer to Section [3.1](#).
- Subjects will be hospitalized on Day -1 (one day before drug administration) and will be discharged on Day 3 only after a formal assessment and confirmation of fitness by an investigator or qualified designee. During in-house confinement, subjects will be under close medical observation and thoroughly monitored for both, expected and unexpected AEs.
- Only if the respective dose of BI 730357 was safe and showed acceptable tolerability and if no stopping criterion was met (refer to Section [3.3.4.3](#)), the next higher dose will be given at least 7 days later (referring to the 1st subject of each dose group).

Since preclinical data indicate that BI 730357 has potential for phototoxicity, subjects will be advised to apply protection measures such as sunscreen, and solarium radiation are prohibited during this clinical trial until the end of the respective follow-up period.

BI 730357 was determined *in vitro* to be a substrate, an inactivator, and an inducer of , as well as an inducer of , thus there is a potential risk of clinically relevant drug-drug interactions (DDI) occurring. Whether substrates will need to be excluded/monitored in subsequent clinical trials will be determined based on results of planned the DDI trials.

Although rare, a potential for drug-induced liver injury (DILI) is under constant surveillance by sponsors and regulators. Therefore, this trial requires timely detection, evaluation, and follow-up of laboratory alterations in selected liver laboratory parameters to ensure subjects' safety, see also Section [5.2.6.1.4](#).

As with other therapies, impaired toxicity, potentially resulting in increased risk of play an important role in IL-17 are associated with . Homozygous, but not heterozygous of T cell lymphoma, thought to originate in the thymus of the phenotype to pharmacological RORY this raises the hypothetical concern for clinical T cell lymphoma risk. The exact cause of T cell lymphomas in mice is not fully understood, but changes in homeostasis in the thymus, such as thymocyte apoptosis and proliferation, are thought to play a role. AEs and SAEs consistent with malignancy, and specifically those representing lymphoma, are to be carefully monitored and evaluated throughout the BI 730357 clinical development program, and monitoring of peripheral blood lymphocyte subsets integrated into clinical trials.

In summary, BI 730357 has the potential to become an oral treatment. Based upon preclinical and clinical data for BI 730357 to date, as well as the implemented safety measures described above, healthy subjects will not be exposed to undue risks in relation to

Proprietary confidential information © 2018 Boehringer Ingelheim International GmbH or one or more of its affiliated companies

the important information expected from this trial as a basis for further clinical development of this compound. Healthy volunteers are not expected to have any direct benefit from participation in this Phase I clinical trial with BI 730357, as is the usual case in such Phase I trials. Considering the medical need of the development of a safer and more effective treatment for patients with PsO, the sponsor considers that the benefit outweighs the potential risks and justifies exposure of healthy human volunteers.

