2. The time is approximate; the respective procedure is to be performed and completed within 3 hours prior to drug administration. Allocation to treatment may be performed at any time following enrolment but must be completed prior to drug administration.
3. If several actions are indicated at the same time point, the intake of meals will be the last action.
4. EOS examination to be performed within 1-4 days after last PK sampling; includes physical examination, vital signs, ECG, safety laboratory, recording of AEs and concomitant therapies.

Proprietary confidential information © 2018 Boehringer Ingelheim International GmbH or one or more of its affiliated companies

5. AEs and concomitant therapies will be recorded throughout the trial, but will be specifically asked for at the time points indicated in the [Flow Chart](#) above. Concomitant therapy is prohibited in this trial (refer to [Section 4.2.2.1](#)) but will be recorded if taken.
6. Safety laboratory, drug screening and alcohol breath test will be performed on admission to be medically evaluation. If those tests are performed within 2 days prior to admission, they can be omitted.
7. The ECG recording has to be performed in triplicate at this time point
8. Sampling times and periods may be adapted based on information obtained during the trial (e.g., preliminary PK data)
9. It is monitored for at least 15 min before drug administration (for baseline assessment) and for 4 hours following drug administration)

  

11. Blood pressure (BP), pulse rate (PR), body temperature, and respiratory rate (RR).
12. Procedures on Days 4, 5 and 8 to be performed within  $\pm 3$  hours from planned time
13. Only drug screening and alcohol test

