### **3. DESCRIPTION OF DESIGN AND TRIAL POPULATION**

#### **3.1 OVERALL TRIAL DESIGN AND PLAN**

This SRD trial is designed as double-blind, randomised within dose group, and placebo-controlled within parallel dose groups.

A total of 24 Japanese healthy male subjects is planned to participate in the trial, according to 3 sequential groups comprising 8 subjects per dose group.

Within each dose group, 6 subjects will receive the active drug and 2 will receive placebo. Only one dose is tested within each dose group.

The dose groups to be evaluated are outlined in Table 3.1: 1 below.

Table 3.1: 1                    Dose groups

Dose Group	1	2	3
Dose (mg)	50	100	200
Number of subjects	8	8	8
Subjects receiving placebo	2	2	2
Subjects receiving active drug	6	6	6

The dose groups will be investigated consecutively in ascending order of doses, maintaining a time interval of at least 7 days between the last drug administration in the previous dose group and the first drug administration of the subsequent dose group.

The decision to proceed to the next dose group will be based upon the safety and tolerability data of the preceding dose groups. The next dose group will only be dose if, in the opinion of the investigator, no safety concerns arose in the preceding dose group(s) (i.e., no dose-limiting events occurred) and if none of the pre-specified trial-specific stopping criteria were met (refer to Section [3.3.4](#)).

A documented safety review must take place prior to randomization in the next group. Furthermore, an unscheduled safety review meeting can be requested anytime for any reasonable cause by the principal investigator (or an authorised deputy) or the sponsor of the study, e.g., because of any unforeseen AEs, etc. Dose escalation will only be permitted if no safety concerns exist in the opinion of the principal investigator (or an authorised deputy) and the sponsor.

The minimum data set for review consists of the following data:

- AEs in the current and preceding dose group(s) (including clinically relevant findings from ancillary safety testing listed below) (Note: AEs may be ongoing at the time of Safety Reviews and AE information may be subject to change prior to Database Lock)
- Results from 12-lead EGG and 4-hours continuous 3-lead ECG monitoring in the current and preceding dose groups.

- Vital signs in the current and preceding dose groups
- Clinical laboratory tests in the current and preceding dose groups

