### **3.3 SELECTION OF TRIAL POPULATION**

It is planned that 24 Japanese healthy male subjects will enter the study. Subjects will be recruited at the trial site.

Only male subjects will be included into the study.

A log of all subjects enrolled into the trial (i.e., having given informed consent) will be maintained in the ISF at the investigational site irrespective of whether they have been treated with investigational drug or not.

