Substrates	Plasma glucose	x	x	x	x
	Creatinine	x	x	x	x
	Blood Urea Nitrogen (BUN)	x	x	x	x
	Total bilirubin	x	x	x	x
	Direct bilirubin	x	x	x	x
	Total protein	x	x	x	x
	Albumin	x	x	x	x
	C-Reactive Protein (CRP)	x	x	x	x
	Uric acid	x	x	x	x
	Total cholesterol	x	x	x	x
	Triglycerides	x	x	x	x
Electrolytes	Sodium	x	x	x	x
	Potassium	x	x	x	x
	Calcium	x	x	x	x

Table 5.2.3: 1 Routine laboratory tests (cont).

Functional lab group	Test name	SCR	A 	B 	EOS
Urinalysis (strip of dipstick)	Urine nitrite	x	x	--	x
	Urine protein	x	x	--	x
	Urine glucose	x	x	--	x
	Urine ketone	x	x	--	x
	Urobilinogen	x	x	--	x
	Urine bilirubin	x	x	--	x
	Urine erythrocytes	x	x	--	x
	Urine leukocytes	x	x	--	x
	Urine pH	x	x	--	x
Urine sediment 	Only positive findings will be reported (for instance, the presence of sediment bacteria, casts in sediment, squamous epithelial cells, erythrocytes, leukocytes)	x	x	--	x

SCR: screening, EOS: end of study

1 A: parameters to be determined at Visit 2 on Day -3 to -1, Day 1, 2, 8 (for time points refer to [Flow Chart](#))

2 B: parameters to be determined at Visit 2, after 4 hours on Day 1 (for time points refer to [Flow Chart](#))

3 Only if erythrocytes, leukocytes nitrite or protein are abnormal in urine and are deemed clinically necessary by the investigator

The tests listed in Table 5.2.3: 2 are exclusionary laboratory tests which may be repeated as required. The results will not be entered in the CRF/database and will not be reported in the CTR. Infection serology test will be planned during screening only. Drug screening and alcohol test will be performed at screening and prior to treatment period.

Proprietary confidential information © 2018 Boehringer Ingelheim International GmbH or one or more of its affiliated companies

Table 5.2.3: 2      Exclusionary laboratory tests

Functional lab group	Test name
Drug screening (urine)	Amphetamine/MDA Barbiturates Benzodiazepine Cannabis Cocaine Methadone Methamphetamines/MDMA/XTC Opiates (Morphine) Phencyclidine Tricyclic antidepressants
Infectious serology (blood)	Hepatitis A antibodies (qualitative) Hepatitis B surface antigen (qualitative)  Hepatitis B surface antibody (qualitative)  Hepatitis B core antibody (qualitative)  Hepatitis C antibodies (qualitative) HIV-1 and HIV-2 antigen and/or antibody (qualitative) QuantiFERON TB-Gold or T-SPOT  Syphilis test (RPR, TP antibody method)

Alcohol test

Breath alcohol test

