## 6. GENERAL ANALYSIS DEFINITIONS

### 6.1 TREATMENTS

It is planned that in total 24 Japanese healthy male subjects participate in this study, according to 3 sequential groups comprising 8 subjects per group. Within each dose group, 6 subjects will receive the active drug and 2 will receive placebo.

For details of dosage and formulation see Table 6.1: 1 below.

Table 6.1: 1 Labels for treatments for use in the CTR

Dose group	Treatment	Short label
1-3	P*	Placebo, tablet, qd
1	A	BI 730357, tablet, 50 mg, qd
2	B	BI 730357, tablet, 100 mg, qd
3	C	BI 730357, tablet, 2*100 mg, qd

\*: The placebo group in the safety evaluation will consist of all placebo treated subjects, regardless of the dose group in which they were treated.

The following separate study phases will be defined for the analyses of AEs:

- **Screening** (ranging from 0:00h (midnight) on day of informed consent until administration time of study drug (BI or Placebo))
- **On treatment**
  - **BI/Placebo treatment** (separately for each treatment, including residual effect period (REP); i.e. ranging from the time of administration of BI 730357 or Placebo until 7 days thereafter or until 0:00h (midnight) on the day after trial termination date (whatever occurs first))
- **Follow-up** (separately for each treatment, ranging from end of on treatment phase until 0:00h (midnight) on the day after trial termination date) – labelled with FU Plc, FU 50mg, FU 100mg, and FU 200mg

Two types of AE displays will be provided in the report:

**A)** Section 15.3 and Appendix 16.1.13.1.8 (for ClinicalTrials.gov) of the CTR displays:

In these displays, the on treatment phase will be analysed (labelled with the name of the study treatment (short label)). Screening and Follow-up will not be included in this analysis.

The following totals will be provided in addition:

- a total over all BI treated phases ("BI Total")
- a total over all on treatment phases included in this analysis ("Total on treatment") (Section 15.3 only)

**B)** Section 15.4 and Appendix 16.1.13.1.8 (except for ClinicalTrials.gov) of the CTR displays:

- Screening
- On treatment (labelled with the name of the study treatment (short label))
- Follow-up

In Section 16.1.13.1.8 AE tables, the following totals will be provided in addition:

- a total over all BI treated phases ("BI Total")
- a total over all study phases ("Total")

Tables of vital signs, ECG and laboratory values will present results by the above mentioned on treatment phase.

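### Do the two descriptions of the 7-day escalation interval, and an undated list of review data, leave the gate between dose groups unsafe?

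*Protocol*

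**What the plan says.** The interval appears twice in the protocol. Among the safety measures of the benefit-risk section (1.4), "the next higher dose will be given at least 7 days later (referring to the 1st subject of each dose group"), provided the current dose was safe and acceptably tolerated and no stopping criterion was met. In the design section (3.1), the groups run in ascending order with "at least 7 days between the last drug administration in the previous dose group and the first drug administration of the subsequent dose group".

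Section 3.1 also sets the gate itself: "A documented safety review must take place prior to randomization in the next group". Its minimum data set covers adverse events, 12-lead and continuous ECG, vital signs, a check of the subject-level stopping criteria, and "Clinical laboratory tests in the current and preceding dose groups". No day or hour is attached to the laboratory item. The investigator and the sponsor take the decision together on the safety data then available, and the review is minuted and signed off.

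On laboratory timing, Table 5.2.3: 1 lists "parameters to be determined at Visit 2 on Day -3 to -1, Day 1, 2, 8", plus a 4-hour set on Day 1. The Flow Chart puts the Day 8 sample at 168:00, with a window of 3 hours either side. It plans randomisation at -3:00, and footnote 2 adds: "Allocation to treatment may be performed at any time following enrolment but must be completed prior to drug administration". Section 3.3 describes subjects as "enrolled into the trial (i.e., having given informed consent").

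**The concern.** There are two worries.

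The first is the anchor. Read alone, Section 1.4 seems to count from the first subject of one group to the first subject of the next. Section 3.1 counts from the last subject dosed. If a group were dosed over several days, the Section 1.4 count would let the next dose level start less than 7 days after the last subject's dose. That would fall inside the period which SAP Section 6.1 treats as on treatment, "ranging from the time of administration of BI 730357 or Placebo until 7 days thereafter". No sentence says which count takes precedence.

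The second is the data cut-off, and it does not depend on how many days a group takes to dose. The review must come before randomisation, but nothing says whether the Day 8 laboratory results of the last-dosed subjects must be in hand. The previous scheduled sample is at 24 h. A review could therefore tick every item on the list while holding nothing later than 24 h on those subjects' liver enzymes, although the stopping criteria to be checked include liver thresholds. Footnote 2 seems to widen the gap, because it allows allocation soon after consent.

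What would be at stake is subject safety at the step to the next dose level.

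**Working it through.** The plan states no figure for this point, so the check is timing arithmetic plus a comparison of the passages.

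**Inputs**
- Minimum interval: 7 days = 7 × 24 = 168 h (Protocol 1.4 and 3.1).
- Scheduled post-dose safety laboratory samples before the end-of-study visit: 4 h, 24 h and 168 h (Flow Chart; Table 5.2.3: 1).
- Day 8 window: 168 − 3 = 165 h to 168 + 3 = 171 h (Flow Chart footnote 12; Section 6.1).
- Planned randomisation: 3 h before dosing (Flow Chart).
- Days from the first to the last dosing within a group, *d*: not given. This is an assumption, shown here for 0 to 3.

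**Step 1. The interval**

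Time from the last dose in one group to the first dose in the next:

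| *d* (days) | Section 1.4 alone, first-to-first reading: 168 − 24*d* | Section 3.1 |
|---|---|---|
| 0 | 168 h | 168 h |
| 1 | 144 h | 168 h |
| 2 | 120 h | 168 h |
| 3 | 96 h | 168 h |

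Now reverse the check. A schedule at the Section 3.1 minimum has a first-to-first interval of 168 + 24*d* h. That is at least 168 h for every *d*, so it always meets Section 1.4. The two conditions can be met together, and the schedules that meet both are exactly those that meet Section 3.1. The 144, 120 and 96 h entries describe schedules that Section 3.1 excludes. A compliant site cannot produce them.

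The first-to-first reading is also not certain. The bracket in Section 1.4 may only identify whose dose counts as the start of the next level, namely the first subject of the new group. On that reading the two sections agree.

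**Step 2. The Day 8 result**

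Take Section 3.1 at its exact minimum:
- Planned randomisation falls at 168 − 3 = 165 h after the last dose.
- The earliest permitted Day 8 draw is also at 165 h, which leaves 165 − 165 = 0 h for a result.
- If allocation is left until just before dosing, at most 168 − 165 = 3 h are available.
- The stretch with no scheduled safety laboratory sample is 168 − 24 = 144 h.

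Now let the interval be *x* hours longer than the minimum. Planned randomisation comes *x* h after the earliest permitted draw and *x* − 6 h after the latest one (165 + *x* − 171). As an illustration only, with *x* = 24 it falls 18 h after the window has closed. The overlap is therefore confined to intervals at or near the minimum, or to a review that is deliberately held early.

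**Step 3. Footnote 2**

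It permits early allocation, but it does not remove the Section 3.1 condition that the review precedes randomisation. Earlier allocation needs an earlier review. It does not move the next group's first dose, which stays at 168 h or later after the last dose.

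**The case for a change.** The strongest case for a change rests on the cut-off. A gate for dose escalation should be unambiguous, and this one does not say what must be known about the most recently dosed subjects. Even with the whole group dosed on one day and Section 3.1 followed to the letter, a review at or before 165 h would lack their Day 8 liver values. Basing the decision on the data available describes what is on the table; it sets no floor. The protocol itself stresses timely detection of liver changes, and a clarifying sentence would cost almost nothing.

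The factual part stands: the list names no time point, and nothing else in the protocol supplies one. What does not follow is that the escalation rule fails. The protocol leaves the sufficiency of the data to a joint decision of the investigator and the sponsor. Either can call an unscheduled review, and either can decline to escalate. Section 3.3.4.3 interrupts randomisation and dosing for defined related serious or severe events. Section 3.1 also notes that adverse events may still be open at the review, so it is designed to run on data to date. In addition, the dose range is not new: Section 1.4 reports single doses up to 800 mg, four times the 200 mg maximum here, and Section 1.2.5 reports up to 400 mg for up to 28 days.

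The argument from the residual effect period does not stand. In the SAP the 7 days assign adverse events to a study phase; no passage makes them an escalation criterion. Section 3.1 in any case keeps the next group's first dose at or beyond 168 h.

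**Conclusion.** No change to the plan follows. The difference between Sections 1.4 and 3.1 is a slip of wording with no effect on any permitted schedule: the minimum after the last dose is 168 h whatever the dosing span. This rests only on the site complying with both sections.

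The missing laboratory cut-off is an unstated detail that the sponsor and investigator settle when they date the review. It matters in two situations: when the interval is at or close to the exact minimum (0 h for a Day 8 result at planned randomisation, at most 3 h before dosing), or when the review is held early by choice. The documents show neither being planned, though they exclude neither.

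The primary endpoint, the pharmacokinetic endpoints, the analysis sets and the sample size are untouched. The two interval sentences, and the status of Day 8 data in the review, could be brought into line when the protocol is next edited. The interval, its anchor and the time point are for the sponsor to choose, and this review takes no view on them.

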## **2. TRIAL OBJECTIVES AND ENDPOINTS**

### **2.1 MAIN OBJECTIVES, PRIMARY AND SECONDARY ENDPOINTS**

#### **2.1.1 Main objectives**

The main objective of this trial is to investigate the safety and tolerability of BI 730357 in Japanese healthy male subjects following oral administration of single rising doses of 50 mg, 100 mg, and 200 mg.

Secondary objectives are the explorations of the PK, including dose proportionality as well as investigation of linearity of BI 730357 after single dose administration.

A description of the endpoints to be determined, and the observations along with specific information as how to collect the data for that information, is provided in Section [5](#).

#### **2.1.2 Primary endpoint**

Primary endpoint to assess safety and tolerability of BI 730357 is the number [N (%)] of subjects with drug-related adverse events.

#### **2.1.3 Secondary endpoints**

The following pharmacokinetic parameters will be determined if feasible:

- $AUC_{0-\infty}$  (area under the concentration-time curve of the analyte in plasma over the time interval from 0 extrapolated to infinity)
- $C_{max}$  (maximum measured concentration of the analyte in plasma)

